8.5 Other Exploratory Analyses

SPID0-24, SPID0-48, SPID0-72, at rest and while standing will be compared between study leg and non-study leg conditional on each of treatment groups based on a mixed model. The model will include treatment, type of leg, treatment by type of leg interaction, and gender as fixed effects and baseline eVAS score as a covariate. A compound symmetry covariance structure will be used to account for correlation between study leg and non-study leg within same subject. The LS mean difference between study leg and non-study leg, SE, p-value and the associated 95% CI will be computed for each of the treatment group.

If any other exploratory analyses or any subgroup analyses are performed after the SAP finalized, they will be documented in Clinical Study Report (CSR).

9 SAFETY EVALUATION

9.1 Overview of Safety Analysis Methods

All safety outcomes will be summarized using the safety population. Safety outcomes include:

- Incidence of treatment-emergent AEs (TEAEs)
- Changes from baseline in clinical laboratory test results
- Changes from baseline in vital sign measurements
- Changes from baseline in physical examinations
- Changes from baseline in ECG findings
- Skin Examination (Study gel application site reaction)
- Residue Evaluation

CONFIDENTIAL

9.2 Adverse Events

Treatment-emergent AE is defined as an AE that begins after the start of study gel or an event that begins before the start of the study gel and worsens in intensity after starting treatment. Verbatim terms used by investigators to identify AEs in the CRFs will be mapped to the appropriate preferred (PT) and system organ class (SOC) using a standardized coding dictionary (MedDRA Version 21.0 or higher). All coding will be reviewed prior to database lock. All recorded AEs/SAEs and TEAEs will be summarized and listed for each treatment group.

In addition to a listing of all TEAEs, separate listings of subjects with SAEs and listings of subjects with severe, treatment related, and AEs leading to premature discontinuation will be provided.

An overall summary will be produced for each treatment group of both the number of events and the number of subjects with TEAEs, SAEs, TEAEs by severity, TEAEs by relationship to treatment, and TEAEs leading to premature discontinuation.

The incidence of TEAEs will be summarized for each treatment group by SOC and PT within SOC (sorted in descending order by overall frequency). These summaries will be given in separate tables for the following categories of TEAEs:

- All TEAEs
- TEAEs leading to premature discontinuation
- SAEs

Also summarized will be TEAEs by maximum severity and by maximum relatedness to treatment. Adverse events will be deemed treatment related if they were recorded as probably, possibly, or definitely related.

If a given subject experiences a TEAE that maps to the same PT more than once, the subject will be counted once for the PT at its greatest severity (i.e., mild, moderate, or severe) and causality (i.e., attribution to study medication).

Duration of an AE will be computed in days (or in hours when duration of the AE is less than 1 day) as the stop date/time of the event minus the start date/time plus 1. If reported as ongoing at the time of database lock, the stop date/time is defined as the date/time of the last visit or the last date/time of any AE for the subject in the database, whichever is later. If an AE is considered resolved, but the stop date is missing, the last day of the month will be imputed if the month and year are available. If only the year is available, and the year is the same as the year of the last visit, the stop date will be the latest of the last visit date or latest AE for the subject in the database. If the year of the AE is prior to the year of the last treatment, the end day and month will be set to 31 December.

For missing or partial start dates, it is most conservative to impute them as temporally related to the first dose of study medication. The following chart will be used to impute start date:

CONFIDENTIAL Page 21 of 33

Missing Portion	Prior to Treatment	Same as Treatment Start Date	After Treatment Start Date
Day	Month and Year < Month and Year of first treatment:	Month and Year = Month and Year of first treatment:	Month and Year > Month and Year of First Treatment:
	Start Day = first day of the month	Start Day = Day of first treatment	Start Day = first day of the month
	Stop Day = last day of the month	Stop Day= last day of the month	Stop Day= last day of the month
Day and Month Define Day as above, then:	Year < Year of first treatment:	Year = Year of first treatment:	Year > Year of first treatment:
	Start Month = July	Start Month =	Month = January
	Stop Month = Dec	Month of first treatment	Stop Month = Dec
		Stop Month = Dec	
Day, Month, and Year	To be conservative, completely missing start dates will be set to the date of first treatment, completely missing end dates will be set to the date of last contact.		
Time	Missing start times will be imputed as 00:01 (or the start time of the first dose administration if AE occurred on the date of first dose administration)		
	Missing stop times will be	imputed as 23:59	

After following these imputation rules, if the start date is imputed as a date after the end date, the start date will be set to the end date to provide a positive duration for the AE.

Missing assessments for AE study medication relationship, or severity will be analyzed as related, severe, and associated, respectively. No other imputation is planned for safety data unless otherwise specified below

9.3 Deaths, Serious Adverse events, and Other Significant Adverse Events

A serious adverse event (SAE) is defined as an event that may constitute a significant medical CONFIDENTIAL Page 22 of 33

hazard or side effect, regardless of the investigator or sponsor's opinion about its relationship to study material. Serious events include, but may not be limited to, any event that:

- Is fatal
- Is life-threatening (places the subject at immediate risk of death while the event is occurring)
- Requires inpatient hospitalization or prolongs hospitalization
- Results in persistent or significant disability/incapacity
- Is a congenital anomaly/birth defect
- Important medical event

Significant untoward medical events that may not be life-threatening or result in death or hospitalization, or events that require intervention to prevent one of the outcomes listed above or that result in urgent investigation, may be considered serious. Elective hospitalizations for conditions that existed before administration of study material are not to be considered SAEs. Serious adverse events and deaths will be listed and summarized separately for the safety population.

9.4 Clinical Laboratory Evaluation

Clinical laboratory samples will be collected at screening, and EOS (as applicable). For continuous laboratory parameters, the observed values and changes from baseline will be summarized for each treatment group. For categorical laboratory parameters, frequency counts and percentages of subjects in each category will be provided.

Laboratory test results will be displayed in by-subject listings, and values outside of the normal reference range will be flagged.

Drug and alcohol screening and pregnancy results will be displayed in by-subject listings.

9.5 Vital Signs, Physical Measurements, and Physical Examinations

9.5.1. Vital Signs and Physical Measurements

Vital signs will be collected at screening, Day 1 prior to study gel administration (Day -1), Day 1, 2 (period 1), Day 8, 15 (period 2), and at the end of study visit on Day 8 or 22 (± 1 day).

Observed values and changes from baseline will be summarized using mean and change-from-baseline descriptive statistics for each treatment group, for the following measurements: systolic blood pressure (mmHg), diastolic blood pressure (mmHg), pulse rate (beats/minute), and oral body temperature. Blood pressure and pulse rate will be measured after the subject has been resting in the supine position for at least 5 minutes.

CONFIDENTIAL Page 23 of 33

Body weight and height will be measured, and BMI will be calculated during the screening visit only. These values will be summarized along with other baseline characteristics for each treatment group. The number and percentage of subjects with potential clinically significant findings listed in Table 2 will be summarized for each treatment group. Vital signs will be displayed in a by-subject listing.

Table 2. List of Potential Clinically Significant Ranges for Vital Sign Parameters

Variable Name	Low	High
Systolic blood pressure	≤86 mm Hg OR a decrease of ≥25 mm Hg from baseline	≥200 mm Hg OR an increase of ≥25 mm Hg from baseline
Diastolic blood pressure	≤48 mm Hg OR a decrease of ≥20 mm Hg from baseline	≥110 mm Hg OR an increase of ≥20 mm Hg from baseline
Pulse	<45 bmp¹ OR a decrease of ≥25 bpm from baseline	>105 bpm and increase ≥25 bpm from baseline OR >125 bpm

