5.2.3 Vital Signs

Vital sign measurements will include systolic blood pressure, diastolic blood pressure, pulse rate, respiratory rate, and oral body temperature. Blood pressure and pulse rate will be measured after the subject has been resting in the supine position for at least 5 minutes. Measurements will be performed according to the schedule in [Table 2](#).

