11.6 ANALYSIS OF SAFETY DATA

The safety endpoint data will be summarized for the safety set.

The AEs will be coded using the latest version of Medical Dictionary for Regulatory Activities (MedDRA). A general summary of the AEs and SAEs will be summarized by overall number of AEs, severity and relationship to study gel, per treatment group. The number of AEs leading to discontinuation/withdrawal and SAEs leading to death will also be summarized. The incidence of AEs will be summarized by body system and treatment group. The incidence of TEAEs will also be summarized by system organ class and preferred term.

The clinical laboratory data will be summarized by treatment group, along with changes from the baseline. The values that are below the lower limit or above the upper limit of the reference range will be flagged. Those values or changes in values, which are identified as being clinically significant, will be flagged.

Vital signs will also be summarized by treatment group and time point, along with the changes from baseline.

All AE, clinical laboratory, vital sign, physical examination, study gel application site reaction, study gel use and concomitant medication use will be presented in data listings.

[REDACTED]

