Table 14.5.1.4	Summary of Categorical Urinalysis Results by Time Point (by Treatment Arm)	Safety Population

CONFIDENTIAL Page 30 of 33

Table 14.6.1	Summary of Vital Signs: Results and Change from Baseline by Time Point (by Treatment Arm)	Safety Population
Table 14.6.2	Summary of Potential Clinically Significant Vital Sign Parameters (by Treatment Arm)	Safety Population
Table 14.7.1	Summary of Physical Examination Results (by Treatment Arm)	Safety Population
Table 14.8.1	Summary of ECG Results (by Treatment Arm)	Safety Population
Table 14.9.1	Summary of Skin Examination (Dermal Responses and Other Effects) (by Treatment Arm)	Safety Population
Table 14.9.2	Summary of Skin Examination (Dermal Responses and Other Effects) (by Treatment Assignment)	Safety Population
Table 14.10.1	Summary of Study Drug Compliance (by Treatment Arm)	Safety Population
Table 14.11.1	Subject's Impression of Dried White Gel Residue (by Treatment Arm)	Safety Population

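### SAP 9.5.1 leaves respiratory rate out of the arm summaries that the protocol plans, and Table 14.6.2 would pool level-based, change-based and already-present vital-sign flags in one count (minor)

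*SAP*

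**What the plan says.** **Respiratory rate.** Protocol 5.2.3 reads "Vital sign measurements will include systolic blood pressure, diastolic blood pressure, pulse rate, respiratory rate, and oral body temperature", and Protocol 2.5 lists the same five among the safety endpoints. Protocol 11.6 plans the analysis: "Vital signs will also be summarized by treatment group and time point, along with the changes from baseline". SAP 9.5.1 then enumerates what will be summarised for each treatment group: systolic pressure, followed by "diastolic blood pressure (mmHg), pulse rate (beats/minute), and oral body temperature". Respiratory rate is not in that list.

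**Flag rules.** SAP 9.5.1, Table 2, has a low and a high cell for systolic pressure, diastolic pressure and pulse. Systolic pressure is flagged high at "≥200 mm Hg OR an increase of ≥25 mm Hg from baseline" and low at "≤86 mm Hg OR a decrease of ≥25 mm Hg from baseline". The two diastolic cells have the same form, with limits of 110 and 48 mm Hg and a change of 20 mm Hg. Low pulse is "<45 bmp¹ OR a decrease of ≥25 bpm from baseline". High pulse is ">105 bpm and increase ≥25 bpm from baseline OR >125 bpm". The section counts subjects with any such finding by group, and the planned output is Table 14.6.2. SAP section 3 defines baseline as the last valid reading before dosing.

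**The concern.** These are two separate matters.

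First, a vital sign that the protocol names as a safety measure, and undertakes to summarise by arm, drops out of the SAP's list without comment. If the programmers follow 9.5.1 literally, it appears only in the by-subject listing.

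Second, Table 14.6.2 is the only threshold summary of vital signs in the planned list of tables. Under its rules three different subjects count alike: one who newly crosses an absolute limit, one who moves a long way between two ordinary values, and one who was beyond a limit before gel and stayed there. A reader who sees, say, a difference of a few subjects between arms cannot tell which of these produced it.

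**Working it through.** The documents state no expected flag rate, so there is no planned figure to reproduce. The first two steps need only the text. The third rests on assumed values.

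**1. Respiratory rate, documents side by side.** Protocol 5.2.3: systolic, diastolic, pulse, respiratory rate, temperature (five). SAP 9.5.1: systolic, diastolic, pulse, temperature (four). SAP section 3 has a general rule that continuous assessments are summarised by time point, but it also says that a specific section prevails where it departs from the general policy. The explicit list in 9.5.1 is such a section.

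**2. Logic of Table 2.**

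- Five cells use a plain OR: systolic low and high, diastolic low and high, pulse low. The high-pulse cell needs more than 105 bpm AND a rise of at least 25 bpm, with more than 125 bpm as an alternative.
- Change alone is enough in the five cells. Systolic 104 to 130 is a rise of 26 and is flagged high. Pulse 82 to 57 is a fall of 25 and is flagged low. The mirror image, pulse 57 to 82, is a rise of 25 and is not flagged, because 82 does not exceed 105.
- Level alone is enough too, even when nothing changed. Pulse 44 before and 44 after gel is flagged.
- The high-pressure level limits add little to the change limits. 200 − 25 = 175, so any reading of 200 or more from a baseline of 175 or less already meets the change limit. 110 − 20 = 90 gives the same result for diastolic pressure from a baseline of 90 or less. Subjects are aged 18 to 35 with no clinically relevant vital-sign abnormality at screening.
- The low limits can act on their own, from baselines below 86 + 25 = 111 mm Hg (systolic), 48 + 20 = 68 mm Hg (diastolic) and 44 + 25 = 69 bpm (pulse).

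**3. Chance flag rate.** All means and SDs here are assumptions. Means (between-subject SD): systolic 118 (10), diastolic 72 (7), pulse 68 (9). Within-subject SD of one reading (systolic/diastolic/pulse): low 5/4/5, middle 8/6/7, high 10/8/10. There is no treatment effect and no time trend.

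For one post-baseline reading with within-subject SD s, the change from baseline has SD s√2, so P(|change| ≥ c) = 2 × [1 − Φ(c/(s√2))].

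- Systolic, c = 25: c/(s√2) = 3.54, 2.21, 1.77, giving 0.04%, 2.7%, 7.7%.
- Diastolic, c = 20: 3.54, 2.36, 1.77, giving 0.04%, 1.8%, 7.7%.
- Pulse, fall of 25 only (one tail): 3.54, 2.53, 1.77, giving 0.02%, 0.6%, 3.9%.

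For all rules together, 400,000 simulated subjects had one baseline and either 2 or 4 later readings. These numbers correspond to 1-week and 3-week subjects if the Day 1 reading is taken before gel, which the SAP does not state.

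| Assumed SD | Flagged at least once (2 to 4 readings) | Expected of 126 | Of those flagged, change limit only |
|---|---|---|---|
| Low | 2.9% to 4.5% | 3.6 to 5.7 | 9% to 11% |
| Middle | 15% to 25% | 19 to 32 | 62% to 63% |
| High | 39% to 58% | 50 to 74 | 65% to 69% |

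The figure 126 is the number in the final analysis (SAP 2.2.6). The trial mixes both durations, so its expectation lies between the two ends of each row.

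In the low-SD case, 21% to 26% of flagged subjects had a reading beyond an absolute limit that they also met at baseline. The high-pressure level limits decided a flag, without the change limit being met, in at most 121 of 400,000 simulated subjects.

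**The case against.** **A change-or-level rule is a legitimate screen.** The findings are labelled potential, and a large within-subject shift inside the normal range is what a change limit is meant to catch. This stands. The OR is not an error.

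**A reader might infer that the table counts mostly measurement noise.** The documents do not support that. The simulation contains no true changes, so every flag in it is chance by construction. It gives a chance flag rate, not the noise share of the real table. Even the share of change-only flags moves from about a tenth to about two thirds across the assumed SDs.

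**A reader might infer that a haemodynamic signal would be hidden.** It would not be. Table 14.6.1 gives results and change from baseline by time point and arm, Listing 16.2.7.2 gives individual values, and Protocol 9.1 has clinically meaningful abnormal test findings recorded as adverse events. Chance flags fall on both arms alike, so they dilute a comparison rather than bias it.

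**A reader might want both limits required for the headline count.** That would redefine the finding and nearly empty the high-pressure cells: systolic 110 to 199 mm Hg would not count. Suppose a true shift of +10 mm Hg and an SD of change of 8.5 to 12.7 mm Hg. The rate of rises of 25 or more per reading goes from 1 − Φ(25/8.5) = 0.2% and 1 − Φ(25/12.7) = 2.5% to 1 − Φ(15/8.5) = 3.9% and 1 − Φ(15/12.7) = 11.9%. The SAP's rule would show that shift, whereas a both-limits rule would hardly register it.

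**Respiratory rate may be summarised anyway.** Table 14.6.1 is titled for vital signs generally, so a summary is possible. That is a reason to settle the wording, not to leave it.

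The low-pulse cell carries a footnote marker whose text is not in the available copy, so a qualification to that cell cannot be ruled out.

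**Conclusion.** Two limited points hold, both from the text alone. The SAP's list omits respiratory rate, which the protocol names and plans to summarise by arm. Table 14.6.2 pools level flags, change flags and limits already met before gel, and its high-pulse cell follows a different logic from the other five without explanation.

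The size of the second point is uncertain. The chance-flag rate runs from about 3% to 58% of subjects, depending on assumed within-subject variability and on 2 or 4 later readings. That range supports showing the components separately. It supports neither a statement about what the real table will contain nor a change of the headline definition. This is a minor point about descriptive safety output in a trial already stopped for futility, and it does not touch the primary analysis.

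**What to change.** 1. Add respiratory rate to the measurements listed in SAP 9.5.1 and to Table 14.6.1, or state why the protocol's plan is not followed.
2. Keep all limits in Table 2 and the existing count. In Table 14.6.2 add, for each parameter and direction: (a) absolute limit met after baseline and not met at baseline, (b) change limit met, (c) both met.
3. State that only post-baseline readings count, and say whether the Day 1 reading is before or after the first gel application.
4. Ask the sponsor to explain the high-pulse construction or reconcile it with the other cells.

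The cost is SAP wording and some extra rows in one descriptive table. No new data are needed. The only drawback is a slightly longer table.

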9.6 Physical and Skin Examinations

Physical examinations are performed at screening, Day 1 prior to study gel administration (Day - 1), Day 1, 2 (period 1), Day 8, 15 (period 2), and at the end of study visit on Day 8 or 22 (± 1 day).

Findings are recorded as normal or abnormal. Physical exam results will be displayed in a bysubject listing.

Skin examination will be performed according to the schedule in Table 2 of the protocol. Dermal responses collected from skin examination CRF will be displayed in a by-subject listing using following rating scales.

Subjects who choose to discontinue from participating in the study will rate their dermal response in the e-diary. Dermal Responses scored by subjects will not be recorded in the eCRF.

CONFIDENTIAL Page 24 of 33

Dermal Responses

- 0 = no evidence of irritation
- 1 = minimal erythema, barely perceptible
- 2 = definite erythema, readily visible; minimal edema or minimal papular response
- 3 = erythema and papules
- 4 = definite edema
- 5 = erythema, edema, and papules
- 6 = vesicular eruption
- 7 = strong reaction spreading beyond application site

Notes: Papules are defined as solid, circumscribed skin elevations up to the size of a split pea (5 mm). Vesicles are defined as small blisters.

Other Effects (With Corresponding Numeric Score)

- None (0) = no change in appearance
- A (0) = slightly glazed appearance
- B (1) = marked glazed appearance
- C (2) = glazing with peeling and cracking
- F(3) = glazing with fissures
- G (4) = film of dried serous exudates covering all or part of the application site
- H (5) = small petechial erosions and/or scabs

9.7 12-Lead Electrocardiogram (ECG)

A 12-lead ECG will be performed at screening, Day 1 prior to study gel application, as well as at the end of study visit on Day 8 or 22 (± 1 day).

The findings (i.e., classification as "normal," "abnormal not clinically significant," or "abnormal clinically significant") will be recorded in the subject's eCRF. ECG results will be summarized for each treatment group and displayed in a by-subject listing.

9.8 Residue Evaluation

To evaluate the subject's impression of the dried white gel residue, the following rating scale will be assessed before the fifth and sixth study gel applications on Day 2 and will be recorded on the appropriate form. Subjects must not shower, bathe, or wash the treated area until after discharge on Day 2.

[figure not shown]
The following rating scale will be used:

CONFIDENTIAL Page 25 of 33

- 0 = No dried white residue was observed
- 1 = Dried white residue was observed but no discomfort.
- 2 = Dried white residue was observed and slight discomfort (between 1 and 3)
- 3 = Dried white residue was observed and uncomfortable

10 PHARMACOKINETIC EVALUATION

Not applicable for this study.

CONFIDENTIAL Page 26 of 33

13 APPENDICES

13.1 Planned Tables, Figures and Listings for Analysis

13.1.1 Tables

Table Number	Table Title	Population	
Subject disposition and baseline characteristics			
Table 14.1.1.1	Summary of Subject Disposition (by Treatment Arm)	All Subjects Screened	
Table 14.1.1.2	Summary of Subject Disposition (by Treatment Assignment)	All Subjects Screened	
Table 14.1.2	Summary of Protocol Deviations (by Treatment Arm)	Randomized Subjects	
Table 14.1.3.1.1	Summary of Demographics and Baseline Characteristics (by Treatment Arm)	Full Analysis Set	
Table 14.1.3.1.2	Summary of Demographics and Baseline Characteristics (by Treatment Assignment)	Full Analysis Set	
Table 14.1.3.2.1	Summary of Demographics and Baseline Characteristics (by Treatment Arm)	Per Protocol Set	
Table 14.1.3.2.2	Summary of Demographics and Baseline Characteristics (by Treatment Assignment)	Per Protocol Set	
Table 14.1.4	Summary of Medical History by System Organ Class and Preferred Term (by Treatment Arm)	Full Analysis Set	
Table 14.1.5	Summary of Concomitant Medications, by ATC Class and Preferred Term (by Treatment Arm)	Full Analysis Set	
Efficacy Evaluations			
Table 14.2.1.1	Primary Endpoint: ANCOVA Results of Summed Pain Intensity Difference from T0 to T24 (SPID0-24) for the study leg while standing (by Treatment Arm)	Full Analysis Set	
Table 14.2.1.2	Primary Endpoint: ANCOVA Results of Summed Pain Intensity Difference from T0 to T24 (SPID0-24) for the study leg while standing (by Treatment Arm)	Per Protocol Set	
Table 14.2.2.1	ANCOVA Results of Sum of Pain Intensity Difference (SPID) 0-12, 0-24, 0-48, 0-72,	Full Analysis Set	
Table 14.2.2.2	ANCOVA Results of Sum of Pain Intensity Difference (SPID) 0-12, 0-24, 0-48, 0-72,	Full Analysis Set	

CONFIDENTIAL Page 28 of 33

	Deposted Magazinas Anglysis Describe of Come of Deliv	
Table 14.2.2.3	Repeated Measures Analysis Results of Sum of Pain Intensity Difference (SPID) 0-12, 0-24, 0-48, 0-72, for K-285 Group	Full Analysis Set
Table 14.2.2.4	Repeated Measures Analysis Results of Sum of Pain Intensity Difference (SPID) 0-12, 0-24, 0-48, 0-72, for K-285 Group	Full Analysis Set
Table 14.2.2.5	Repeated Measures Analysis Results of Sum of Pain Intensity Difference (SPID) 0-12, 0-24, 0-48, 0-72, for Menthol Group	Full Analysis Set
Table 14.2.2.6	Repeated Measures Analysis Results of Sum of Pain Intensity Difference (SPID) 0-12, 0-24, 0-48, 0-72, for Menthol Group	Full Analysis Set
Table 14.2.2.8	Primary Endpoint: ANCOVA Results of Summed Pain Intensity Difference from T0 to T24 (SPID0-24) for the Study Leg while Standing (by Treatment Arm) – Each Multiple Imputed Dataset	Full Analysis Set
Table 14.2.3.1		Full Analysis Set
Table 14.2.3.2		Full Analysis Set
Table 14.2.4.1		Full Analysis Set
Table 14.2.4.2		Full Analysis Set
Table 14.2.5.1		Full Analysis Set
Table 14.2.5.2		Full Analysis Set
Table 14.2.8.1		Full Analysis Set

CONFIDENTIAL Page 29 of 33

	·	
Table 14.2.9.1	Proportion of subjects with onset of perceptible pain relief between 0 to 6 hours, 0 to 24 hours for study leg while standing and at rest (by Treatment Arm)	Full Analysis Set
Table 14.2.9.2	Proportion of subjects with onset of meaningful pain relief between 0 to 6 hours, 0 to 24 hours for study leg while standing and at rest (by Treatment Arm)	Full Analysis Set
Table 14.2.10	Summary of Rescue Medication (by Treatment Arm)	Full Analysis Set
	Safety Evaluations	
Table 14.3.1.1.1	Overall Summary of Treatment-Emergent Adverse Events (by Treatment Arm)	Safety Population
Table 14.3.1.1.2	Overall Summary of Treatment-Emergent Adverse Events (by Treatment Assignment)	Safety Population
Table 14.3.1.2.1	Summary of Treatment Emergent Adverse Events by System Organ Class and Preferred Term (by Treatment Arm)	Safety Population
Table 14.3.1.2.2	Summary of Treatment Emergent Adverse Events by System Organ Class and Preferred Term (by Treatment Assignment)	Safety Population
Table 14.3.1.4.1	Summary of Treatment Emergent Adverse Events by System Organ Class, Preferred Term, and Severity (by Treatment Arm)	Safety Population
Table 14.3.1.4.2	Summary of Treatment Emergent Adverse Events by System Organ Class, Preferred Term, and Severity (by Treatment Assignment)	Safety Population
Table 14.3.1.5.1	Summary of Treatment Emergent Adverse Events by System Organ Class, Preferred Term, and Relationship to Study Drug (by Treatment Arm)	Safety Population
Table 14.3.1.5.2	Summary of Treatment Emergent Adverse Events by System Organ Class, Preferred Term, and Relationship to Study Drug (by Treatment Assignment)	Safety Population
Table 14.5.1.1	Summary of Chemistry Results and Change from Baseline by Time Point (by Treatment Arm)	Safety Population
Table 14.5.1.2	Summary of Hematology Results and Change from Baseline by Time Point (by Treatment Arm)	Safety Population
Table 14.5.1.3	Summary of Continuous Urinalysis Results and Change from Baseline by Time Point (by Treatment Arm)	Safety Population
Table 14.5.1.4	Summary of Categorical Urinalysis Results by Time Point (by Treatment Arm)	Safety Population

CONFIDENTIAL Page 30 of 33

Table 14.6.1	Summary of Vital Signs: Results and Change from Baseline by Time Point (by Treatment Arm)	Safety Population
Table 14.6.2	Summary of Potential Clinically Significant Vital Sign Parameters (by Treatment Arm)	Safety Population
Table 14.7.1	Summary of Physical Examination Results (by Treatment Arm)	Safety Population
Table 14.8.1	Summary of ECG Results (by Treatment Arm)	Safety Population
Table 14.9.1	Summary of Skin Examination (Dermal Responses and Other Effects) (by Treatment Arm)	Safety Population
Table 14.9.2	Summary of Skin Examination (Dermal Responses and Other Effects) (by Treatment Assignment)	Safety Population
Table 14.10.1	Summary of Study Drug Compliance (by Treatment Arm)	Safety Population
Table 14.11.1	Subject's Impression of Dried White Gel Residue (by Treatment Arm)	Safety Population

